1. INTRODUCTION

77242113PSO2001 is a randomized, double-blind, placebo-controlled, dose-ranging, parallel group, multicenter, interventional study in participants with moderate-to-severe plaque psoriasis.

At Week 16 of 77242113PSO2001 study, eligible participants will have the option to enroll in a 36-week treatment long term extension (LTE) study (77242113PSO2002); all participants will be treated with active study intervention in the LTE.

This Statistical Analysis Plan (SAP) contains definitions of analyses sets, derived variables and address the statistical methods for all planned analyses for both 77242113PSO2001 (through the Week 16 Database lock (DBL)) and 77242113PSO2002 (through Week 40 database lock) studies as 77242113PSO2002 study is the long term extension (LTE) study of the original study (77242113PSO2001)

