Furthermore, assuming PASI 75 response rates at Week 16 are 5% to 10% for placebo, 30% to 80% for the JNJ-77242113 dose groups, respectively, with 40 participants in each of the treatment groups, approximately 240 participants are planned to be randomized in equal ratio to the placebo and each of JNJ-77242113 dose groups (n=40/arm), this study provides:

At least 90% power to detect a 35% treatment difference between the JNJ-77242113 treatment groups (n=40) and the placebo group (n=40) in the proportion of participants who achieve a PASI 75 response at Week 16 at a significant level of 0.05 (2-sided) based on a 2-sample Z-test.

3.2. 77242113PSO2002

Protocol 77242113PSO2002 is the LTE study of Protocol 77242113PSO2001, therefore there is no formal calculation of the sample size for study 77242113PSO2002. The sample size of this LTE study will be determined by the number of participants who enroll in study 77242113PSO2001 and are eligible to enter and choose to participate in this LTE study.

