For selected subject's information and all safety analyses, combined data from 77242113PSO2001 and 77242113PSO2002 studies for participants initially randomized to JNJ-77242113, and who crossed over and received JNJ-77242113 for participants initially randomized to placebo will be included. In addition, safety data from 77242113PSO2002 data will also be summarized for randomized participants in 77242113PSO2001 who entered the long-term extension study 77242113PSO2002 and received at least one dose of study intervention (including a partial dose) during the 77242113PSO2002 study period. For efficacy and PK/PD analyses, efficacy and PK/PD data from 77242113PSO2001 and 77242113PSO2002 studies will be included and summarized.

The populations for analysis are defined in [Table 4](#) below.

Table 4: Population for analysis for 77242113PSO2002

Population	Description
FAS	Randomized participants who received at least one dose of study intervention in the originating study (77242113PSO2001) for participants initially randomized to JNJ-77242113, and participants who crossed over and received JNJ-77242113 for participants initially randomized to placebo
Safety Analysis Set	Randomized participants who received at least one dose of study intervention in the originating study (77242113PSO2001) for participants initially randomized to JNJ-77242113, and participants who crossed over and received JNJ-77242113 for participants initially randomized to placebo
LTE Safety Analysis Set	The LTE safety analysis set consists of randomized participants in 77242113PSO2001 who entered the long-term extension study 77242113PSO2002 and received at least one dose of study intervention (including a partial dose) during the 77242113PSO2002 study period
PK Analysis Set	All participants in 77242113PSO2001 or 77242113PSO2002 who received at least 1 complete dose of JNJ-77242113 and had at least 1 valid blood sample drawn for PK analysis after their first dose of JNJ-77242113
Immunogenicity Analysis Set	All participants in 77242113PSO2001 or 77242113PSO2002 who received at least 1 dose of JNJ-77242113 and who had at least 1 sample obtained after the first dose of JNJ-77242113 for the detection of antibodies to JNJ-77242113

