5.1.3.2. Study 77242113PSO2002

Efficacy summaries for 77242113PSO2002 study will be based on the pooled data from both 77242113PSO2001 and 77242113PSO2002 studies, FAS (Section 4.2) will be used and participants will be summarized and presented by randomized treatment group at Week 0 of 77242113PSO2001 study:

- **Placebo→: JNJ-77242113 100 mg QD:** Participants randomized to placebo group at Week 0.
 - Only participants crossed over to receive JNJ-77242113 100 mg QD at Week 16 will be included in the summary for the visits after Week 16.
- **JNJ-77242113 25 mg QD:** Participants randomized to 25 mg QD group at Week 0.
- **JNJ-77242113 50 mg QD:** Participants randomized to 50 mg QD group at Week 0.
- **JNJ-77242113 25 mg BID:** Participants randomized to 25 mg BID at Week 0.
- **JNJ-77242113 100 mg QD:** Participants randomized to 100 mg QD at Week 0.
- **JNJ-77242113 100 mg BID:** Participants randomized to 100 mg BID at Week 0.

For the efficacy overtime analyses that combines the 77242113PSO2001 and 77242113PSO2002 studies, Week 4 visit of the study 77242113PSO2002 will be aligned as Week 20 for the combined study and will be denoted as “Week 20 (LTE Week 4)” in the summary table; similar notation will be applied for the subsequent visits of the study 77242113PSO2002.

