5.3.2.3. Analysis Methods for Primary Estimand

The primary efficacy analysis for study 77242113PSO2002 will be based on the FAS defined in Section 4.2. Since there is no control arm (placebo), in this primary analysis, only the proportion of participants who achieve a PASI75 response and its 95% confidence interval at Week 36 will be summarized for each intervention group.

The data handling method specified in Section 5.3.1.2.3 will be applied. More specifically, participants with ICEs 1-2 before Week 36 will be considered as PASI75 non-responders at Week 36. Participants with ICE 3, observed PASI data after this ICE will be utilized in the analysis. After accounting for the ICEs for the primary estimand, participants with the missing data of the primary endpoint at Week 36 will be considered as non-responders.

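### In the extension's responder analyses, active-arm participants who do not enter PSO2002 count as non-responders, so a fall after Week 16 can reflect non-entry and not loss of response

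*SAP*

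**What the plan says.** - **Analysis set, active arms** (SAP 4.2, Table 4): "Randomized participants who received at least one dose of study intervention in the originating study (77242113PSO2001) for participants initially randomized to JNJ-77242113". Nothing requires a dose in PSO2002.
- **Analysis set, former placebo arm** (same row of Table 4): "participants who crossed over and received JNJ-77242113 for participants initially randomized to placebo". SAP 5.1.3.2 repeats the limit, "Only participants crossed over to receive JNJ-77242113 100 mg QD at Week 16 will be included in the summary for the visits after" Week 16, and sets no such limit for the active columns.
- **Use of the set** (SAP 5.3.2.3): "The primary efficacy analysis for study 77242113PSO2002 will be based on the FAS defined in" Section 4.2.
- **Missing data** (SAP 5.3.2.3): "participants with the missing data of the primary endpoint at Week 36 will be considered as non-responders". SAP 5.4.2.2.3 carries this to the binary secondary endpoints, and SAP 5.5.2.2 uses the same set and the corresponding handling for the over-time tables through Week 52.
- **Entry is optional and conditional** (SAP 1): "eligible participants will have the option to enroll in a 36-week treatment long term extension (LTE) study". SAP 3.2 sizes the extension by those who are "eligible to enter and choose to participate in this LTE study".
- **No second efficacy analysis.** PSO2002 has one estimand (SAP 5.3.2.2.1), which does not mention non-entry, and no supplementary or sensitivity analysis. Table 4 does define a set of participants dosed in PSO2002, the LTE Safety Analysis Set, but SAP 4.2 reserves it for safety.

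**The concern.** The primary objective of the extension is long-term clinical response to treatment, and the Week 36 proportion with its confidence interval in each group is the whole primary result. In the active columns that proportion mixes two things: whether participants on continued treatment keep their response, and whether they were eligible and willing to enter a second protocol. A participant can complete PSO2001 clear of psoriasis, attend the Week 20 safety visit, meet the protocol's definition of a study completer (Protocol 4.4), and still be a treatment failure at Week 36 of the extension. A placebo participant who does not enter simply leaves the denominator.

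The reading at stake is maintenance of response. A drop between Week 16 and the extension visits in the combined tables would naturally be taken as waning effect on continued treatment. Because the extension is descriptive, with no tests, readers have only these percentages to go on.

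**Working it through.** The plan gives no figure to reproduce here: SAP 3.2 states that PSO2002 has no formal sample size calculation, and neither document gives an expected entry rate. The check traces the rules and then sizes their effect.

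**Step 1. Follow a non-entrant through the rules.**

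| | Active arm | Placebo arm |
|---|---|---|
| In the PSO2002 FAS? | Yes (dosed in PSO2001) | No (did not cross over) |
| Week 36 PASI 75 value | None | Not applicable |
| Counted as | Non-responder | Not counted |

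**Step 2. Size of the effect.** Let *q* be the proportion who respond, the same in entrants and non-entrants, and *d* the share of an active arm's FAS that never enters. The FAS reports *q*(1 − *d*); an entrants-only denominator reports *q*; the gap is *q* × *d*. For *q*, take the SAP 3.1 planning range for active groups, 30% to 80%. For *d*, 5% to 20% is an assumption. Gap in percentage points:

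| *q* | *d* = 5% | 10% | 15% | 20% |
|---|---|---|---|---|
| 30% | 1.5 | 3.0 | 4.5 | 6.0 |
| 50% | 2.5 | 5.0 | 7.5 | 10.0 |
| 70% | 3.5 | 7.0 | 10.5 | 14.0 |
| 80% | 4.0 | 8.0 | 12.0 | 16.0 |

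With 40 per arm, each would-be responder who stays out costs 1/40 = 2.5 points, whatever the entry rate.

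**Step 3. Dependence on who stays out.** Take 40 dosed, 28 responders at Week 16 (70%), 4 non-entrants, and response fully maintained in entrants.

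- Non-entry unrelated to response: 4 × 0.70 = 2.8 responders lost on average; Week 36 in the FAS = 25.2/40 = 63.0%; among entrants 25.2/36 = 70.0%.
- All four were Week 16 non-responders: 28/40 = 70%, so no fall.
- All four were Week 16 responders: 24/40 = 60%, a 10-point fall with no loss of response.

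The fall therefore comes only from Week 16 responders who do not enter. Participants with intercurrent events 1 or 2, or with missing Week 16 data, are already non-responders at Week 16 and add nothing to it.

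**Step 4. Would an entrants-only set make 100 mg QD and placebo-to-100 mg QD comparable?** Entry requires completing PSO2001 through Week 16 (SAP Figure 2, footnote). Assume that on either path 10% of those starting active drug stop within their first 16 weeks on it, 70% of starters respond later, and everyone else who can enter does. Among entrants, 100 mg QD shows 70/90 = 77.8%, because its early stoppers are gone. The crossover group keeps its early stoppers and shows 70/100 = 70%. That is a gap of about 8 points in the other direction. In addition, at LTE Week 36 the 100 mg QD group has had 16 + 36 = 52 weeks on drug and the crossover group 36.

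**Step 5. Reach.** The mechanism applies to binary endpoints. Continuous endpoints use MMRM without imputation (SAP 5.4.2.2.3), so non-entrants are not set to failure there. One detail is open: the PSO2001 schedule collects PASI at the Week 20 follow-up visit, off treatment, and the SAP does not say whether that value fills the combined Week 20. The step could first show at Week 20 or at the next visit; Week 36 is unaffected.

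**The case against.** The strongest defence is that Table 4 follows one coherent rule: everyone is included from the start of active drug. For the active arms that is Week 0 of PSO2001; for placebo participants it is the crossover. A placebo participant who never crossed over never took JNJ-77242113 and cannot be a failure of it. Counting missing as failure is then a conservative choice, and some non-entrants stopped for lack of efficacy or worsening, whom the composite strategy means to count as failures. The extension has no hypothesis and plans no between-group comparison. SAP 5.2 already plans disposition by group and a listing of participants who did not enter. The full entry rules sit in a separate protocol that is not among these documents.

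Most of this stands, and it is why the planned analysis should remain primary. It does not answer the maintenance question: a Week 16 responder who completes PSO2001 and goes no further has not lost response, and no planned table separates that person from one who has.

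Three stronger readings are tempting and are not supported:

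- *A false fall will appear in every active arm.* It needs Week 16 responders who do not enter, and the documents do not say how many there will be.
- *The dose ordering is distorted.* The five active arms share one rule; their order shifts only if entry rates differ.
- *100 mg QD should be read against placebo-to-100 mg QD only among entrants.* Step 4 shows that this swaps one imbalance for another.

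**Conclusion.** The point holds as an inexpensive improvement to a descriptive analysis. The SAP text makes an active-arm non-entrant a non-responder at extension visits without data, including Week 36, while the crossover column contains only entrants, and no planned efficacy analysis isolates the effect. The damage is to interpretation, not to type I error.

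The size is conditional. It is about 1.5 to 16 points under non-entry of 5% to 20%, unrelated to response, with response of 30% to 80%. Only the response range comes from the SAP; the non-entry range and its independence from response are assumptions. The effect is zero if no would-be responder fails to enter. Not all of the gap is artefact, since participants with intercurrent events 1 or 2 are failures by design.

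**What to change.** 1. Keep the planned FAS analysis of PSO2002 as primary.
2. In SAP 5.3.2.3, 5.4.2.2.3 and 5.5.2.2, add a supplementary analysis of the primary endpoint, the binary secondary endpoints and the over-time tables in participants dosed at least once in PSO2002. This is the existing LTE Safety Analysis Set, applied to all six columns with the same intercurrent-event and missing-data rules. Use it beside the FAS result when judging maintenance of response after Week 16.
3. In the FAS tables, footnote for each active column the number of non-entrants imputed as non-responders. Separate those with intercurrent events 1 or 2, or already non-responders at Week 16, from Week 16 responders who did not enter.
4. State that neither set makes 100 mg QD and placebo-to-100 mg QD like-for-like: 100 mg QD entrants are selected for completing 16 weeks on drug, and exposure at LTE Week 36 is 52 against 36 weeks.

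The cost is SAP wording and a repeat of planned tables on a set already defined; no new data are needed. The downside is that entrants are a selected group, so both versions must be shown together.

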Unless otherwise specified, all over-time (e.g., Week 0-52) efficacy analyses will be based on the Full Analysis Set (FAS), and safety analyses with cumulative safety data by combining studies JNJ-77242113PSO2001 and JNJ-77242113PSO2002 will be based on the Safety Analysis Set. All LTE-specific safety analyses (include data only from JNJ-77242113PSO2002 study) will be based on the LTE Safety Analysis Set.

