5.6. Safety Analyses

All safety analyses will be performed using safety analysis set based on actual intervention received. No formal statistical comparison is planned.

For all continuous safety variables, descriptive statistics by intervention group will include the N, mean, standard deviation, median, minimum, and maximum. Categorical variables will be summarized by intervention group using frequency counts and percentages.

Depending on the study, the cumulative safety data will be analyzed through different study and study periods as shown below. Unless otherwise specified, tabular summaries of safety events are also presented as following:

Study 77242113PSO2001

The safety data through the end of the main study 77242113PSO2001 will be included and safety analysis set (Section 4.1) will be used. For participants who entered 7242113PSO2002 study at the time of Week 16 visit (without a gap period), safety data through Week 16 are included. For participants who completed the participation of the 77242112PSO2001 study but either had a delay in joining or didn't participate 77242113PSO2002 study, safety data through end of the study are included. Safety data through the end of the 77242113PSO2001 study will be summarized by following intervention group:

- Placebo
- JNJ-77242113 25 mg QD
- JNJ-77242113 50 mg AD
- JNJ-77242113 25 mg BID
- JNJ-77242113 100 mg QD
- JNJ-77242113 100 mg BID
- Combined JNJ-77242113 groups

Study 77242113PSO2002

(a) Safety data from Week 16 (Week 0 of 77242113PSO2002 study) through Week 56 (Week 40 of 77242113PSO2002 study) for participants enter the 77242113PSO2002 will be included and LTE safety analysis set (Section 4.2) will be used. Safety data from Week 16 through Week 56 will be summarized by following intervention group:

- Placebo → JNJ-77242113 100 mg QD
- JNJ-77242113 25 mg QD
- JNJ-77242113 50 mg QD
- JNJ-77242113 25 mg BID
- JNJ-77242113 100 mg QD
- JNJ-77242113 100 mg BID
- Combined JNJ-77242113 groups

(b) Safety data through Week 56 (Week 40 of 77242113PSO2002 study) with the combined data of 77242113PSO2001 and 77242113PSO2002 studies will be included and safety analysis set (Section 4.2) will be used. Safety data through Week 56 will be summarized by following intervention groups.

- Placebo
- Placebo → JNJ-77242113 100 mg QD
- JNJ-77242113 25 mg QD
- JNJ-77242113 50 mg QD
- JNJ-77242113 25 mg BID
- JNJ-77242113 100 mg QD
- JNJ-77242113 100 mg BID
- Combined JNJ-77242113 groups

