5.6.3. Additional Safety Assessments (if applicable)

5.6.3.1. Clinical Laboratory Tests

Clinical laboratory tests will be displayed for the participants included in the safety analysis set.

Descriptive statistics and graphical displays will be presented for selected chemistry and hematology laboratory tests at scheduled time points.

Change from baseline through different study periods in both studies as specified in Section 5.6 will be summarized for chemistry, and hematology tests and displayed by intervention group. Box plots of laboratory measurements and change from baseline will be provided for the selected laboratory measurement.

- **Hematology** will include but are not limited to the following: Basophils, Eosinophils, Hemoglobin, Lymphocytes, Monocytes, Neutrophils, Platelets, WBC, CRP and ESR.
- **Chemistry** will include but are not limited to the following: ALT, AST, Albumin, Alkaline Phosphatase, Bicarbonate (CO₂), Corrected Calcium, Chloride, Creatinine, GGT, Glucose, Potassium, SGOT, SGPT, Sodium, Total Bilirubin, Total Protein, Urea Nitrogen.

Applicable laboratory results will be graded according to National Cancer Institute's Common Terminology Criteria for Adverse Events (NCI-CTCAE). The proportion of participants with post-baseline values by maximum toxicity grade for clinical laboratory tests will be summarized by study intervention group. Participants with toxicity grades ≥ 2 will be listed.

In addition, for selected laboratory parameters, ULN will also be used to identify abnormal laboratory test results, and the incidence and severity of abnormal laboratory parameters (hematology and chemistry) will be summarized by treatment group. Participants with maximum post-baseline elevated liver function tests through Week 16 (77242113PSO2001) and through Week 56 relative to ULN will be summarized in categories as shown below will be provided.:

- $> 1 \times$ ULN
- $\geq 3 \times$ ULN
- $\geq 5 \times$ ULN
- $\geq 10 \times$ ULN

- $\geq 20 \times \text{ULN}$

In addition, Summary of potential Hy's Law case (ALT or AST $\geq 3 \times \text{ULN}$ and total bilirubin $\geq 2 \times \text{ULN}$) through Week 16 and Week 56 respectively will also be provided.

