Suicidal ideation and behavior will be summarized based on the most severe/maximum post baseline C-SSRS outcome or AE of suicidal ideation, suicidal behavior excluding completed suicide, or completed suicide through Week 16 for 77242113PSO2001 study or through Week 56 (Week 40 of the 77242113PSO2002 study), and from Week 16 (Week 0 of the 77242113PSO2002) through Week 56 (Week 40 of the 77242113PSO2002 study) for participants in the 77242113PSO2002 study period. In addition, frequency distribution of the most severe/maximum post baseline C-SSRS outcome will be tabulated by C-SSRS categories and intervention group through Week 16 and through Week 56. The baseline is defined as the most severe/maximum C-SSRS score at either screening or Week 0.

The maximum score assigned for each participant will also be summarized into one of three broad categories: No suicidal ideation or behavior, suicidal ideation, suicidal behavior. A shift table for change in C-SSRS categories of no suicidal ideation or behavior, suicidal ideation, and suicidal behavior from baseline through Week 16 for study 77242113PSO2001 and through 56 for the

combined 77242113PSO2001 and 77242113PSO2002 studies, and from Week 16 through Week 56 for participants in the 77242113PSO2002 study period will be presented, where the baseline category is based on C-SSRS score form study 77242113PSO2001 and the post baseline is based on C-SSRS or AE data.

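### The Week 56 safety tables list a Placebo column, but their analysis set leaves out placebo participants who never crossed over

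*SAP*

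**What the plan says.** Three parts of the SAP bear on this.

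- **Who is in the combined set.** The opening paragraph of 4.2 covers all safety analyses. For the placebo arm it takes participants "and who crossed over and received JNJ-77242113 for participants initially randomized to placebo will be included". Table 4 repeats the condition in the Safety Analysis Set: "participants who crossed over and received JNJ-77242113 for participants initially randomized to placebo". Participants randomized to active drug need only one dose in PSO2001.
- **Where the set is used.** The text after Table 4 says that "safety analyses with cumulative safety data by combining studies JNJ-77242113PSO2001 and JNJ-77242113PSO2002 will be based on the Safety Analysis Set". Section 5.6, PSO2002 part (b), points back to the 4.2 set and states: "Safety data through Week 56 will be summarized by following intervention groups". The list that follows begins with Placebo and then gives Placebo to 100 mg QD as a separate column.
- **What the Week 16 tables use.** Table 3 in 4.1 defines the PSO2001 Safety Analysis Set as every randomized participant who took a dose. For participants who finished PSO2001 but entered the extension late or not at all, 5.6 adds that "safety data through end of the study are included".

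Several summaries are produced at both horizons. On laboratory data, 5.6.3.1 says "Clinical laboratory tests will be displayed for the participants included in the safety analysis set", and the potential Hy's Law summary "through Week 16 and Week 56 respectively will also be provided". The C-SSRS frequency distribution "will be tabulated by C-SSRS categories and intervention group through Week 16 and through Week 56".

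**The concern.** Membership of the combined set depends on what happened during the placebo period, and it does so for the placebo arm only. A participant on active drug who stops for an adverse event at Week 6 stays in the Week 56 table. A placebo participant who does the same never crosses over and is left out. The column most readers will use as the reference would then hold only participants who went on to extension dosing, next to active columns that include early stoppers.

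The second problem is agreement between tables. A cumulative count should not fall as follow-up lengthens, but here the placebo N, event counts and average follow-up through Week 56 can differ from those in the PSO2001 tables, with nothing in the SAP to explain why. The SAP also does not say which events and which follow-up time belong in which of the two placebo columns.

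**Working it through.** The plan states no figure on this point, so there is none to reproduce. The check compares the definitions and then works out denominators.

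**Definitions side by side**

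| | PSO2001 safety tables | Combined tables through Week 56 |
|---|---|---|
| Set | SAP 4.1, Table 3 | SAP 4.2, Table 4 |
| Active arms | all dosed | all dosed in PSO2001 |
| Placebo arm | all dosed | crossed over and received active drug |
| Placebo columns (5.6) | Placebo | Placebo; Placebo to 100 mg QD |

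**What the Week 56 Placebo column can contain.** If it means the crossovers' data before crossover, non-enterers are missing. If it means participants who only ever received placebo, Table 4 leaves it empty. Neither reading restores the non-enterers. Nothing in 4.2 or 5.6 does so, and Appendix 2 (changes to protocol-planned analyses) is marked not applicable.

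**Why early stoppers are unlikely to cross over.** The footnote to SAP Figure 2 links extension eligibility to having completed PSO2001 through Week 16. Protocol 6.6 says study intervention is not made available again after a discontinuation under Section 7.1. Protocol 4.4 counts an extension enrollee as a completer only if all scheduled dosing through Week 16 was taken. For liver events, Protocol 10.9.1 requires discontinuation when the stopping criteria are met, and 10.9.2.1 rules out restarting. A placebo participant with a potential Hy's Law finding before Week 16 would therefore be counted in the Week 16 summary and be absent from the Week 56 one.

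**Denominators.** Planned placebo N is 40 (SAP 1.2.1). The documents give no non-entry rate and no placebo rate of discontinuation for adverse events, so the rates below are assumptions.

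- Non-entry of 5%: 0.05 × 40 = 2 excluded, N = 38. Non-entry of 20%: 0.20 × 40 = 8 excluded, N = 32.
- Chance that the two placebo Ns differ, if each participant's non-entry probability is 5%: 1 − 0.95^40 = 0.871. At 20%: 1 − 0.80^40 = 0.9999.
- Expected placebo discontinuations for adverse events at 2.5%: 0.025 × 40 = 1. At 5%: 0.05 × 40 = 2. The PSO2001 table would show 1/40 or 2/40, and the Week 56 Placebo column 0.
- Chance of at least one such discontinuation, and so of disagreement on that row: 1 − 0.975^40 = 0.637 at 2.5%; 1 − 0.95^40 = 0.871 at 5%.
- Effect on a common row, if 20 of 40 placebo participants (50%) had any adverse event. The Week 56 figure depends on how many of them are among the excluded:
  - 2 excluded: 18/38 = 47.4% to 20/38 = 52.6%
  - 4 excluded: 16/36 = 44.4% to 20/36 = 55.6%
  - 8 excluded: 12/32 = 37.5% to 20/32 = 62.5%

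With no non-enterers, the two columns hold the same participants and there is no effect.

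**The case against.** The strongest counter-argument concerns intent. SAP 5.1.3.2 applies the 4.2 FAS, whose crossover wording is identical, yet describes the placebo group as those randomized to placebo at Week 0 and restricts it to crossovers only for visits after Week 16. The authors may have meant the same for safety. That supports reading Table 4 as a drafting slip, but 5.1.3.2 governs efficacy summaries only, and a programmer following 4.2 and 5.6(b) would still leave the non-enterers out.

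The entry argument also has limits. The extension's full entry criteria sit in the PSO2002 protocol, which is not among these documents; Protocol 4.4 is a completion definition, not an entry rule; and the SAP foresees delayed entry. It is therefore very unlikely, but not proven impossible, that someone who stopped for an adverse event would cross over. Nor does the sentence in 5.6 on late entrants and non-enterers name early stoppers: they are in the Week 16 tables through Table 3.

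Finally, the consequence is modest. No formal safety comparison is planned, and placebo exposure is about 16 weeks against up to about 52 on active drug, so the columns are not like for like under any set definition. The PSO2001 tables and listings lose no placebo event, and a placebo Hy's Law case is a remote possibility in a group of 40. All of this stands. It limits the weight of the point but does not remove the conflict between the set and the column.

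**Conclusion.** The concern holds. SAP 4.2 and 5.6(b) cannot both be followed and still give a complete Placebo column in the Week 56 safety tables. Read as written, the column is selected on outcome for placebo and not for active drug, and it can disagree with the Week 16 tables.

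The textual conflict is certain; its size is not. It depends on how many placebo participants do not enter the extension, and the ranges given are illustrations on assumed rates. The effect is confined to the descriptive combined tables. The PSO2001 safety tables remain the complete placebo reference, and the primary analysis, type I error and power are untouched. It should be corrected before the combined tables are programmed.

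**What to change.** Reconcile the opening paragraph of 4.2 and Table 4 with 5.6(b), in one of two ways.

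1. Keep the Placebo column and base it on every participant randomized to placebo who took a dose in PSO2001, as in Table 3. State that placebo-period events and follow-up count under Placebo, and post-crossover events and follow-up under Placebo to 100 mg QD.
2. If the combined set is meant to cover only participants exposed to active drug, keep Table 4, remove the Placebo column from the Week 56 tables and refer readers to the PSO2001 tables for placebo.

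At the same time, align the Table 4 FAS with 5.1.3.2: all dosed placebo participants through Week 16, crossovers only afterwards.

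The cost is SAP wording plus one set definition or one column in programming. No new data are needed.
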